16.5 Appendix 5: Approximate amount of blood withdrawn

Table 16-7 Amount of blood withdrawn per Cohort

Cohort	Age of Participants	Amount of blood withdrawn (ml)* from Participants in total study duration
1-2	≥ 12 years	~40
3	6 years - < 12 years	~40
4	2 years - < 6 years	~11
5	6 months - < 2 years	~11
*Blood volume indicated are approximate. If for any reason additional blood is withdrawn especially due to safety or repeat assessment please ensure to keep it close to micro sampling especially for children, per local regulations.		

16.6 Appendix 6: Coma Scores used in the study

Table 16-8 Glasgow Coma Scale

Eye Opening (E)	-	Verbal Response (V)	-	Best Motor Response (M)	-
Spontaneous	4	Oriented	5	Obedying Commands	6
To speech	3	Confused	4	Localizing	5
To pressure	2	Words	3	Normal flexion	4
None	1	Sounds	2	Abnormal flexion	3
-	-	None	1	Extension	2
-	-	-	-	None	1

Table 16-9 Blantyre Coma Score

Eye Opening (E)		Verbal Response (V)		Best Motor Response (M)	
Able to follow the moving object	1	Normal cry or appropriate speech (for patients who are old enough to talk) in response to painful stimuli	2	Localize pain stimulus	2
Unable to follow the moving object	0	Moan or an abnormal cry in response to painful stimuli	1	Withdraw limb from pain stimulus	1
-	-	No cry with painful stimuli	0	No response or inappropriate response to pain stimulus	0

The purpose of this Statistical Analysis Plan (SAP), is to describe the implementation of the statistical analysis, which is planned in the protocol (Version 00). Mock shells for the clinical study report (CSR) will be prepared according to this SAP. Statistical outputs for the CSR will be generated after the final database lock (DBL) according to this SAP and the mock shells. A separate set of mock shells may be prepared and executed for DMCs based on this SAP.

Any data analysis carried out independently by the investigator should be submitted to Novartis before publication or presentation.

All CSR analyses will be carried out using SAS, Version 9.4 or higher.

1.1 Study design

This will be an adaptive, multicenter, randomized, open label, sequential cohort study in patients aged ≥ 12 years old in Cohorts 1-2 and ≥ 6 months to < 12 years old in Cohorts 3-5 with a diagnosis of moderately severe and severe *P. falciparum* malaria.

The study has five age descending cohorts; Cohorts 1 and 2 (≥ 12 y), Cohort 3 (6y- < 12 y), Cohort 4 (2y- < 6 y), and Cohort 5 (6m- < 2 y).

Cohorts 1 and 2:

[figure not shown]
Patients will be randomized to one of the three treatment regimens in a 1:1:1 ratio. Two cipargamin based regimens will have the dose levels of 20 mg and 40 mg, whereas, the control regimen will be IV artesunate, a standard of care. Cohorts 1 and 2 plan to include 18 and 42 patients aged ≥ 12 years with body weight between 35-75 kg, respectively. The results from Cohorts 1 and 2 will be analyzed to determine the safe and efficacious exposure range and the corresponding doses (cipargamin (KAE609) dose regimen 3) for the patients in Cohorts 3 to 5.

In case of cipargamin dose adaptation, additional patients may be recruited with new dose levels in each cohort to ensure 6 and 14 patients per regimen in Cohorts 1 and 2, respectively.

Cohorts 3-5:

Two treatment regimens based on IV artesunate and IV cipargamin will be selected. Patients will be randomized to one of these regimens in 1:1 ratio. Cipargamin dose is not decided a priori at this time. Cohorts 3-5 include patients with age < 12 years and weight > 5 kg. Cohort 3 includes 38 patients per regimen with age 6- < 12 years; Cohort 4 also includes 38 patients per regimen with age 2- < 6 years; whereas, Cohort 5 includes 20 participants per regimen with age 6 months - < 2 years. Additional patients may be recruited in each cohort after dose modification to ensure designated number of patients on the same cipargamin dose level. After the completion of Cohorts 1 and 2, the DMC have endorsed the following cipargamin dosing schedule for children in Cohorts 3 and 4: 40 mg for body weight ≥ 35 kg, 24 mg for body weight 20 to < 35 kg, 12 mg for body weight 10 to < 20 kg, and 6 mg for body weight 5 to < 10 kg.

Figure 1-1 Study Design

Notes:

KAE609 (Cipargamin)

Moderately severe malaria – Prostration and/or repeated vomiting (Barnes et al 2004)

Study to progress from Cohort 1 to Cohort 2 without interruption if none of the KAE609 arms in Cohort 1 meets the stopping criteria.

*Results from Cohort 1 and Cohort 2 will be analyzed to determine the safe and efficacious exposure range and the corresponding doses (KAE dose regimen 3) for participants in Cohorts 3 to 5.

Doses for Cohort 4 will be confirmed after PK analysis from upto 6 KAE609 participants from Cohort 3 and for Cohort 5, it would be post completion of Cohort 4 .

** Cohort 5 recruitment is dependent on availability of adequate toxicology package to dose down to ≥ 6 m

KAE609 doses across the study will be adaptive depending on the safe and efficacious exposure range identified before the study (for Cohorts 1-2) and after interim assessment of Cohort 1 & 2 (for Cohorts 3-5)

Randomization is stratified within each cohort according to country and previous antimalarial therapy use to achieve the balanced treatment allocation for these stratification factors.

Patients will be admitted to the hospital on Day 1. They will remain in hospital under close supervision until they are discharged by the investigator or designee on Day 4. At the discretion of the investigator, patients may stay for additional days if needed. The patients will then be followed up at Days 6, 8, 15, 22, and 29. Visits to assess safety and efficacy will be scheduled during the follow-up period as described in the schedule of assessments tables (Table 8-1 and Table 8-2) in the protocol.

In all cohorts, patients on IV cipargamin regimens will receive once daily injection of IV cipargamin over a minimum of 2 days and a maximum of 3 days; with IV artesunate as rescue medication. Patients in the IV artesunate regimen will be administered a minimum of 3 doses during the first 2 days of treatment. There is no rescue medication for IV artesunate regimen since it is the standard of care therapy recommended by WHO; however, if the patients are not responding in first 2 days, they will be treated for longer with IV artesunate. Patients in all regimens will receive Coartem BID for 3 days following IV therapy.

1.2 Study objectives and endpoints

Table 1-1 Objectives and related endpoints

Objective(s)	Endpoint(s)
Primary objective(s)	Endpoint(s) for primary objective(s)

 To assess the efficacy of IV cipargamin 	
 Proportion of patients with $\geq 90\%$ P. falciparum parasite reduction at 12 hours, see Section 2.5.1 for the primary estimand
Secondary objective(s)	Endpoint(s) for secondary objective(s)

 To assess clinical outcome 	
 Proportion of patients with clinical success (see Section 2.7.2.1) over time. Clinical success at 48 hours is considered as the key secondary endpoint, see Section 2.6.1 for the secondary estimand.

 To assess the presence/absence of individual signs of severe malaria 	
 Proportion of patients with individual signs of severe malaria over time (see Section 2.7.2.2).

 To assess the risk of hemolysis 	
 Proportion of patients developing hemolysis (early and delayed) after treatment (see Section 2.8.2)

 To assess the risk of long term neurological sequelae 	
 Proportion of patients with neurological sequelae at Day 29 (see Section 2.7.2.3)

 To evaluate parasite clearance dynamics 	
 Proportions of patients with $\geq 90\%$ parasite reduction at 24 and 48 hours PCE slope half-life Time to P. falciparum parasite clearance (PCT) P. falciparum parasite reduction ratios (PRR) at 12, 24 and 48 hours Proportion of patients with recrudescence and reinfection by Day 29 
See Section 2.7.2

 To assess other efficacy endpoints 	
 Time (days and hours) to switch to oral therapy Day of discharge from hospital Time (hours) to recover from prostration 
See Section 2.7.2

 To evaluate the safety and tolerability of IV cipargamin 	
 Standard safety/tolerability assessments (incidence of serious adverse events (SAEs), mortality, in-hospital mortality, adverse events (AEs), and routine safety and laboratory assessments) 
See Section 2.8


 To assess the plasma pharmacokinetics of IV cipargamin 	
 PK parameters of cipargamin: C_{max}, T_{1/2}, AUC, CL and V_z Alpha-1-acid glycoprotein level over time and correlation of AAG concentration with cipargamin PK parameters 
See Section 2.9

Objective(s)	Endpoint(s)
Exploratory objective(s)	Endpoint(s) for exploratory objective(s)
CCI	

2 Statistical methods

2.1 Data analysis general information

Data will be analyzed by Novartis using SAS version 9.4 or higher according to the data analysis presented in Section 12 of the study protocol, which is also available in Appendix 16.1.1 of the CSR. Detailed information is given in the following sections.

Data analyses required for the study Data Monitoring Committee (DMC) will be analyzed by a Novartis internal independent biostatistics team. The outline of the DMC analysis outputs is presented in the DMC charter and will be detailed in a separate mock shell based on this SAP.

Information on visit windowing, imputation rules and the methods of efficacy and safety analyses is given in the sections to follow. This SAP covers the methods for: DMC meetings, planned interim assessment, and the final analysis.

Unless otherwise stated, summary tables/figures/listings will be on all patients included in the population under consideration.

Categorical data will be presented as frequencies and percentages. For continuous data, n, mean, standard deviation, median, 25th and 75th percentiles (for selected parameters), minimum, and maximum will be presented. Additionally, geometric mean will be presented for PK parameters which may be better described using the lognormal distribution.

Unless otherwise stated, p-values (if required) will be provided for two-sided alternative hypotheses and presented up to 4 significant digits after decimal place; confidence intervals will be presented up to 2 significant digits after decimal place.

The dose level of treatment groups in a cohort may be adjusted if a chosen dose is not the optimal dose. Once the dose level has been adjusted, it becomes a different treatment group. If a dose regimen is considered similar among the 5 cohorts, data will be summarized by treatment

group for all 5 cohorts pooled and separately pooled Cohorts 3-5 in addition to summary by cohort and treatment group.

When data from different cohorts are pooled, an IV cipargamin regimen in Cohorts 3 to 5 (aged < 12 years) will be analyzed together with the equivalent IV cipargamin regimen as used in Cohorts 1 and 2 (aged ≥ 12 years). Such an IV cipargamin dose regimen will be denoted and labeled using the same cipargamin treatment group.

Key efficacy and safety data will be summarized separately for adults (aged ≥ 18 years) and children (aged <18 years).

Note: similar doses among 5 cohorts are based on the equivalent adult dose according to the probable weight bands for cohorts 3-5 as defined in protocol. However, they may be reassessed based on PK exposures at the end of study.

All post-text tables will be generated using Microsoft Word cell-based format so that they can be easily cut and pasted to create intext tables for the CSR. For each cohort, some treatment groups may consist sub-optimal dose levels. All treatment groups will be displayed in the post-text tables. However, only those treatment groups containing the dose levels that are deemed to be optimal for each cohort are important for displaying in the intext tables. Therefore, post-text tables will display all cohorts including the pooled cohort (if applicable) and all treatment groups under a cohort side by side as columns.

Randomization is stratified by country and use of any pretreatment of antimalarial drugs before screening period for each cohort. However, due to small sample sizes within a stratum, statistical analysis will not use these strata. For pooled analyses, study cohort (Cohorts 1 and 2 will be pooled together) will be used as stratum.

Parasite evaluations will be done by local microscopists for all the samples. Parasite evaluations will be also done using central laboratory for samples in Cohorts 1 and 2. Local readings will be used for the initial screening and local decisions for management of malaria. The statistical analysis will be performed using local laboratory readings for all cohorts and repeated using central laboratory readings for Cohorts 1 and 2. The identification for out of range *P. falciparum* parasite counts or other species for the exclusion of patients from the analyses sets will be based on local laboratory readings if they are available and central laboratory readings will be used in case of non-availability of the readings from the local laboratory. Both local laboratory and central laboratory readings will be all listed in the CSR appendix.

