6.3.2 Treatment assignment, randomization

At Day 1, all eligible participants will be randomized via Interactive Response Technology (IRT) to one of the treatment arms. The investigator or his/her delegate will contact the IRT after confirming that the participant fulfills all the inclusion/exclusion criteria. The IRT will assign a randomization number to the participant, which will be used to link the participant to a treatment arm and will specify a unique medication number for the first package of study treatment to be dispensed to the participant.

The randomization numbers will be generated using the following procedure to ensure that treatment assignment is unbiased and concealed from participants and investigator staff. A participant randomization list will be produced by the IRT provider using a validated system that automates the random assignment of participant numbers to randomization numbers. These

randomization numbers are linked to the different treatment arms, which in turn are linked to medication numbers. A separate medication list will be produced by or under the responsibility of Novartis Global Clinical Supply (GCS) using a validated system that automates the random assignment of medication numbers to packs containing the study treatment.

Randomization will be stratified by country and if any pretreatment of antimalarial drugs before screening period for each cohort.

The randomization scheme for participant will be reviewed and approved by a member of the Randomization Office.

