2.5.2 Statistical hypothesis, model, and method of analysis

The statistical null hypothesis is that the difference in proportion of patients with $\geq 90\%$ reduction at 12 hours between a cipargamin dose regimen and artesunate is ≤ -0.1 with the alternative hypothesis that the difference is > -0.1 .

The statistical hypothesis will be tested at the 2-sided 10% significance level without multiplicity adjustment for multiple comparison due to multiple cipargamin dose regimen. Two-sided 90% confidence intervals (CI) for the difference between each cipargamin dose regimen vs artesunate will be provided using the Wilson uncorrected method: a cipargamin dose regimen is said to be non-inferior to artesunate if the lower limit of CI is > -0.1 .

The hypothesis will be tested for each Cohort separately except Cohort 1, which will be combined with Cohort 2.

Data from patients in Cohorts 1 and 2 will be pooled together to allow evaluation of non-inferiority to artesunate since both cohorts include patients aged ≥ 12 years although patients in Cohort 1 are milder in clinical condition compared to patients in Cohort 2. The underlying assumptions are (1) the patients for each treatment group follow a binomial distribution separately in each Cohort except Cohort 1, which will be combined with Cohort 2, (2) patients for each treatment group, follow the same binomial distribution in Cohorts 1 and 2.

FAS will be used.

Wilson uncorrected method:

Let

a = # responders in cipargamin arm

c = # non-responders in cipargamin arm

m = sample size of the cipargamin regimen ($a+c$)

b = # responder in the artesunate arm

d = # non-responders in the artesunate arm

n = sample size of the artesunate regimen ($b+d$)

$\theta = \pi_1 - \pi_2$ is the difference between two arms

$\hat{\theta} = a/m - b/n$ is estimated difference between two arms

Method based on the Wilson score method for the single proportion, without continuity correction:

$L = \hat{\theta} - \delta$, $U = \hat{\theta} + \varepsilon$ where

$$\delta = \sqrt{\{(a/m - l_1)^2 + (u_2 - b/n)^2\}} = z\sqrt{\{l_1(1 - l_1)/m + u_2(1 - u_2)/n\}}$$

$$\varepsilon = \sqrt{\{(u_1 - a/m)^2 + (b/n - l_2)^2\}} = z\sqrt{\{u_1(1 - u_1)/m + l_2(1 - l_2)/n\}}$$

l_1 and u_1 are the roots of $|\pi_1 - a/m| = z\sqrt{\{\pi_1(1 - \pi_1)/m\}}$, and l_2 and u_2 are the roots of $|\pi_2 - b/n| = z\sqrt{\{\pi_2(1 - \pi_2)/n\}}$.

Where z is the standard normal deviate associated with 10% level of significance (l.o.s.) two sided.

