2.5.6 Supplementary analysis

For each Cohort (except Cohort 1, which will be pooled with Cohort 2), the difference between a cipargamin dose regimen and artesunate in the proportion of patients with $\geq 90\%$ reduction in parasite at 12 hours will be performed using the Fisher exact test.

For each cipargamin dose regimen that is selected for Cohorts 3-5, the difference versus artesunate in proportion of patients with $\geq 90\%$ reduction in parasite at 12 hours will be evaluated by pooling data from all cohorts to show if the IV cipargamin dose regimen is superior to IV artesunate. The treatment difference will be evaluated based on 2-sided 95% CIs using a Mantel-Haenszel estimate of the common risk difference stratified by cohort (Cohorts 1 and 2 will be pooled together and used as a single stratum)(SAS manual version 13.2). P-values will be provided using a Cochran-Mantel-Haenszel test (CMH) stratified by cohort.

Similarly, between treatment difference will be evaluated in children by repeating the above supplementary analysis on pooled Cohorts from 3-5 only.

A 2-sided 95% CIs for the proportion of patients with achieving primary endpoint for each treatment group will be provided based on the Clopper-Pearson exact method on pooled cohort.

These supplementary analyses target a different hypothesis to show superiority of each cipargamin dose regimen over artesunate and will be performed using the FAS and handling of intercurrent events and missing values not related to intercurrent events according to [Section 2.5.3](#) and [Section 2.5.4](#).

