2.6.2 Statistical hypothesis, model, and method of analysis for secondary estimand

There are no pre-specified hypotheses for secondary endpoints. Model, method of analysis, and handling of missing values/censoring/discontinuations are presented in the following subsection.

The clinical success at 48 hours will be evaluated using the FAS with data from all cohorts pooled.

Intercurrent events and other non-intercurrent events including partial missing data that may occur and affect the derivation of secondary estimand will be handled in [Section 2.6.3](#).

Two-sided 90% CIs for the difference between a cipargamin dose regimen and artesunate will be provided using a Mantel-Haenszel estimate of the common risk difference stratified by cohort where Cohorts 1 and 2 will be combined. Mantel-Haenszel estimate is a weighted risk difference with weight roughly proportional to strata size. It's an unbiased estimation of risk difference in the population under the following assumptions either (1) the risk difference is same across different strata or (2) the strata sizes in study resemble the strata size in the disease

population at large. Two-sided 90% CIs for the difference for the Mantel-Haenszel estimate of the common risk difference will be calculated using the local lab data only.

Descriptive statistics will be provided by cohort using the local lab data in addition to all cohorts pooled. Descriptive statistics will be provided for Cohorts 1 and 2 using the central lab data.

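### The small-strata reason for leaving the randomisation factors out of the analysis does not cover prior antimalarial use in the pooled comparisons; the loss is small and the remedy nearly free

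*SAP*

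**What the plan says.** Protocol 6.3.2 sets the randomisation: "Randomization will be stratified by country and if any pretreatment of antimalarial drugs before screening period for each cohort". SAP 1.1 repeats it: "Randomization is stratified within each cohort according to country and previous antimalarial therapy use".

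SAP 2.1 then departs from it for the analysis: "due to small sample sizes within a stratum, statistical analysis will not use these strata". It continues: "For pooled analyses, study cohort (Cohorts 1 and 2 will be pooled together) will be used as stratum".

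The planned comparisons follow that rule.

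- **Primary, by cohort (SAP 2.5.2):** an unstratified Wilson/Newcombe 90% interval, where "a cipargamin dose regimen is said to be non-inferior to artesunate if the lower limit of CI is > -0.1".
- **Pooled 12-hour superiority, supplementary (SAP 2.5.6):** a Mantel-Haenszel risk difference, and "P-values will be provided using a Cochran-Mantel-Haenszel test (CMH) stratified by cohort".
- **Key secondary, clinical success at 48 hours (SAP 2.6.2):** 90% intervals "using a Mantel-Haenszel estimate of the common risk difference stratified by cohort where Cohorts 1 and 2 will be combined". SAP 2.7.2.1 does the same at other time points.
- **Pooled time-to-event endpoints (SAP 2.7.2.4):** log-rank tests stratified by cohort.
- **Pooled parasite reduction ratio and clearance half-life (SAP 2.7.2.5):** ANCOVA on the log scale with log baseline, treatment and cohort.

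The factors do appear elsewhere. SAP 2.2.1 lists prior antimalarial use, marked as a stratification factor, and region (Africa, Asia) as descriptive subgroups. SAP 2.5.7 and 2.6.6 apply these to the primary and key secondary endpoints. Country is a covariate in the multiple-imputation model of SAP 5.8.4.

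**The concern.** Stratified randomisation balances the arms on the chosen factors. If those factors predict outcome, the treatment difference varies less from trial to trial than an unstratified variance formula assumes. An analysis that ignores them then reports a standard error that is too large, so precision obtained by the design does not reach the interval.

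The SAP gives one reason for ignoring the factors: stratum size. That reason has to be tested separately for the by-cohort and the pooled analyses, because the numbers differ greatly. The pooled key secondary analysis matters most. It was sized on interval width, and its endpoint may become the primary endpoint in Phase III (SAP 3.2).

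**Working it through.** **Inputs from the documents.** Per-arm allocation is 6, 14, 38, 38 and 20 for Cohorts 1 to 5 (SAP 3.2). With Cohorts 1 and 2 combined, the strata are 20, 38, 38 and 20, which sum to 116 per arm, or 232 for two arms. The assumed clinical success rate is 0.75 in both arms (SAP 3.2). The assumed artesunate 12-hour response is 45% (SAP 3.1); the cipargamin rate is redacted.

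**Assumptions.** The documents mention about 20 sites in Africa and Asia (Protocol 5) but not the number of countries, so 5 to 10 equal-sized countries are assumed. Pretreatment prevalence and effect are also assumed.

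**1. The plan's own figure.** Enumerating two binomials at 0.75 with the Newcombe 90% interval, the probability of a half-width of at most 0.1 is 0.838 at n = 107 and 0.790 at n = 106. The stated 107 reproduces. Allowing for 8% exclusion, 107 / 0.92 = 116.3, which agrees with about 116. This sizing used unstratified intervals, so the target does not rely on any covariate gain.

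**2. Stratum sizes.**

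| Analysis | Strata | Average size |
|---|---|---|
| By cohort, country × pretreatment, 5 countries | 10 per cohort | 20/10 = 2.0 to 38/10 = 3.8 per arm |
| By cohort, country × pretreatment, 10 countries | 20 per cohort | 1.0 to 1.9 per arm |
| Pooled, cohort × country × pretreatment | 40 to 80 | 232/40 = 5.8 to 232/80 = 2.9 in total |
| Pooled, cohort × pretreatment | 8 | 232/8 = 29 in total |

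The averages hide uneven cells. At 20% pretreated, the smallest pooled cell holds about 0.2 × 40 = 8 patients, which a Mantel-Haenszel analysis can use.

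**3. Size of the gain.** The proportional fall in the standard error is 1 − √(W/T). Here W = Σ f·p(1 − p) over the pretreatment groups, with f the share and p the response rate in each group, and T = p̄(1 − p̄) with p̄ = Σ f·p.

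- *Clinical success, overall 0.75, odds ratio 2.* At 20% pretreated the rates are 0.842 and 0.727: W = 0.1854, T = 0.1875, fall 0.6%. At 50% pretreated they are 0.814 and 0.686: W = 0.1834, fall 1.1%. A half-width of 0.100 becomes about 0.099.
- *12-hour endpoint, 0.45 in those not pretreated, same rates in both arms.* At 20% pretreated with response 0.65: W = 0.2435, T = 0.2499, fall 1.3%. At 50% pretreated with response 0.75: W = 0.2175, T = 0.2400, fall 4.8%.
- *12-hour endpoint with cipargamin at an assumed 0.85 and the same odds ratios:* 1.0% to 3.9%.

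**4. Simulation of the pooled Mantel-Haenszel 90% interval.** There were 4,000 trials per scenario, with permuted blocks of 4 within cohort × country × pretreatment, 25% pretreated, base rate 0.75 and true difference 0. Ranges are for 5 and 10 countries.

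| Prognostic effect | Cohort only: coverage, half-width | Cohort × pretreatment: coverage, half-width |
|---|---|---|
| None | 0.891–0.893, 0.0931–0.0933 | 0.892–0.893, 0.0933–0.0937 |
| Moderate (pretreatment OR 2, country logits ±0.7) | 0.901–0.907, 0.0948 | 0.895–0.903, 0.0941–0.0943 |
| Strong (pretreatment OR 4, country logits ±1.2) | 0.916–0.918, 0.0972–0.0974 | 0.908–0.913, 0.0941–0.0943 |

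Bias was at most about 0.002 everywhere. Under the strong effect with 5 countries, the estimate's actual spread was almost the same either way (SD 0.0554 and 0.0552). The adjustment mainly brings the reported standard error into line with it (mean SE 0.0592 against 0.0573).

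Full crossing with 10 countries put about 26 of 232 patients in one-arm strata. With no effect it widened the half-width from 0.0933 to 0.1003.

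**The case against.** The case for leaving the plan alone is substantial.

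- The SAP is open about its choice, and the randomisation strata it refers to include country. Crossed in full, they are too sparse even when pooled. **This stands**, and it is why country should not be crossed into the strata.
- Pretreatment may predict little. Antimalarials within 12 hours of screening are an exclusion (Protocol 5.2) and remove a patient from the per-protocol set (SAP 5.9). Correctly enrolled pretreated patients were therefore dosed earlier and still met the parasite-count criterion. The pooled ANCOVA models already adjust for log baseline parasitaemia. **This stands** as a reason to expect a small gain.
- No formal decision depends on the pooled analyses. The 12-hour superiority analysis is supplementary, and the secondary endpoints have no pre-specified hypotheses (SAP 2.6.2, 2.7.2). **This stands.**
- SAP 1.1 reports the dosing schedule endorsed after Cohorts 1 and 2 were completed, and Protocol 6.4 unblinds the trial team to those results at the interim lock. Changing the main strata now would follow unblinding for part of the data. **This stands**, and it shapes the fix.

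None of this supplies a stratum-size reason against 8 strata averaging 29 patients.

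A reader might also infer that both factors are ignored throughout. The subgroup summaries and the imputation model show otherwise. Nor do the documents support an inference that the primary non-inferiority test is biased or invalid: the omission produces no material bias, and within a cohort the strata really are too small.

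**Conclusion.** The point holds in a limited form. No between-treatment comparison is adjusted for country or prior antimalarial use. The stated reason justifies this by cohort and for the full crossing, but not for prior antimalarial use in the pooled Mantel-Haenszel, CMH, log-rank and ANCOVA analyses.

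The consequence is a modest loss of reported precision. At the planned 0.75 success rate with a moderate effect it is about 1% of the standard error. For the 12-hour endpoint it reaches about 5% only under strong assumed effects. It cannot be said that the pooled intervals are too wide as a matter of fact: with no prognostic effect, cohort-only coverage was already 0.89 and there is nothing to recover.

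The sizes rest on assumed prevalence, effect and number of countries, none of which the documents give. Unequal country sizes would make some country strata smaller still. This is an inexpensive improvement and not a threat to the trial's conclusions.

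**What to change.** 1. In SAP 2.1, limit the small-strata statement to the by-cohort analyses and to full crossing with country.
2. For the final analysis, use cohort (1 and 2 combined) by prior antimalarial use as strata in the pooled Mantel-Haenszel and CMH analyses (SAP 2.5.6, 2.6.2, 2.6.5, 2.7.2.1) and in the pooled log-rank tests (SAP 2.7.2.4).
3. Add prior antimalarial use and region (Africa, Asia), already defined in SAP 2.2.1, as factors in the pooled parasite reduction ratio and half-life ANCOVA models (SAP 2.7.2.5). These are two-level factors, so each costs one degree of freedom.
4. Report the cohort-only results alongside, because the plan unblinds the trial team to Cohorts 1 and 2. At minimum, pre-specify the adjusted version as a sensitivity analysis before the final database lock.
5. Leave the by-cohort Newcombe tests unchanged.

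The cost is a few sentences in the SAP and one or two variables, already collected, in existing procedures. If pretreatment has no effect, the simulated half-width rises by 0.0002 to 0.0004.
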